## 7 MEASUREMENTS OF TREATMENT COMPLIANCE

Compliance with BRV study medication will not be assessed in this NIS.

## 8 EFFECTIVENESS ANALYSIS

All effectiveness analyses will be performed on the FAS and the modified FAS, except subgroup analyses that will only be performed on the FAS.

### 8.1 Statistical analysis of the primary variable

#### 8.1.1 Retention at 12 months

Patients who remain in the study and are on BRV treatment 1 year after their start of BRV will be classed as having 12 months of treatment retention. More specifically, a patient will be categorized as having 12 months BRV retention if they do not meet either of the following criteria:

- Date of study termination < date of first BRV administration + 330 days
- Date of last administration of BRV while in the study < date of first BRV administration + 330 days

Otherwise, patients meeting either of the bulleted conditions above will be categorized as not having 12 months BRV retention. Date of last administration of BRV will be derived as described in [Section 3.2.4](#). 330 days is used to represent 1 year of treatment in accordance with the visit window instructions given to sites (i.e., that the 12 month visit should not be prior to 330 days). This is to prevent classing patients as not having BRV retention when in fact they completed the study within 30 days of the target 360 days.

The number and percentage of patients achieving 12 months retention will be presented on the FAS along with a 2-sided exact (Clopper-Pearson) 95% CI for the percentage.

A by-patient listing of patient retention data including dates of first and last BRV administration, date of study termination, time to discontinuation of BRV or study termination, visit window target dates, and retention at 3, 6 (as described in [Section 8.2.1](#)), and 12 months will be listed on the All Subjects Documented set.

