#### **3.2 General study level definitions**

##### **3.2.1 Relative day**

The relative day of a given date “D” will be calculated as follows:

- For days prior to the first BRV administration:  
D – date of first BRV administration
- For days on or after date of first BRV administration and prior to or on the day of last BRV administration:  
D – date of first BRV administration + 1
- For days after the last BRV administration:  
D – date of last BRV administration  
A “+” will be shown at the start to denote posttreatment days

Hence, the first day of BRV administration is Day 1, the day before the first BRV administration is Day -1, and the day after the last dose of BRV is Day +1. Relative day will not be calculated for partial dates.

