## **8.2 Statistical analysis of the secondary variables**

### **8.2.1 Retention at 3 and 6 months**

Similar to the primary endpoint, patients will be classed as having 3 months BRV retention if they do not meet either of the following criteria:

- Date of study termination < date of first BRV administration + 90 days
- Date of last administration of BRV while in the study < date of first BRV administration + 90 days

Otherwise, patients meeting either of the bulleted conditions above will be categorized as not having 3 months BRV retention. 90 days is selected because at least 3 months BRV retention is required, hence a patient who attends a month 3 visit early and terminates BRV prior to Day 90, would not be classed as having 3 months retention.

Patients will be classed as having 6 months BRV retention if they do not meet either of the following criteria:

- Date of study termination < date of first BRV administration + 180 days
- Date of last administration of BRV while in the study < date of first BRV administration + 180 days

Otherwise, patients meeting either of the bulleted conditions above will be categorized as not having 6 months BRV retention. 180 days is selected because at least 6 months BRV retention is required, hence a patient who attends a month 6 visit early and terminates BRV prior to Day 180 would not be classed as having 6 months retention.

BRV Retention at 3 and 6 months will be summarized using the methods described in [Section 8.1](#) for the FAS and the modified FAS. BRV Retention at 3 and 6 months will be listed as described in [Section 8.1.1](#).

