3. Patient had missing seizure data at the visit (or missed the visit) but had not discontinued BRV or terminated the study prior to the visit’s target day [a]. Note: If a patient is ongoing in the study and had not got to the visit yet, they are treated in the same way as having missed visit.	Missing	Missing
4. Patient met none of the above classifications and patient has the visit present	Yes	Yes

[a] The target day for each visit is: Visit 2 (Month 3) = Day 90, Visit 3 (Month 6) = Day 180, and Visit 4 (Month 12) = Day 330. For Month 12 assessments, seizure freedom will be analyzed for completers only. Therefore assign missing to all patients who withdraw for the Month 12 analyses.

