## **10 SAFETY ANALYSES**

### **10.1 Extent of exposure**

The duration of exposure of BRV (days) while in the study is calculated as:

Date of last administration of BRV while in the study – date of first BRV administration + 1.

For snapshot analyses, patients with missing date of last administration of BRV while in the study will be imputed using the date of data cut-off for the analysis. This assumes that patients still ongoing in the trial are still taking BRV.

All exposure analyses will be performed on the SS and the modified FAS.

Exposure will be summarized using descriptive statistics of the continuous variable duration of exposure (days). In addition, the following categories of duration of exposure (days) will show the number of patients with 1 day to <3 months BRV (1-<90 days), 3 months to <6 months BRV (90-<180 days), 6 months to <12 months BRV (180-<330 days), and ≥12 months BRV (≥330 days).

The number and percentage of patients receiving each daily BRV dose at Day 2, Day 7, Day 14, Day 21, Day 30, Day 60, Day 90, Day 120, Day 150, Day 180, Day 240 and Day 330 will be

summarized in the following BRV dose categories ( $\leq 10\text{mg}$ ,  $>10$  to  $<50\text{mg}$ ,  $\geq 50\text{mg}$  to  $<100\text{mg}$ ,  $\geq 100\text{mg}$  to  $<150\text{mg}$ ,  $\geq 150\text{mg}$  to  $\leq 200\text{mg}$  and  $>200\text{mg}$ ). In addition, the total number of patients receiving each Dose category at any time on the study will be presented. Day 1 will be equal to the first BRV administration date. Day 2 is considered as the starting dose due to some patients only receiving 1 dose (afternoon dose only) on Day 1.

Time to BRV maintenance dose will be summarized descriptively and will be defined as:

Date of first intake of the BRV dose the patient remained on for the longest time during the treatment period – Date of first BRV administration.

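### The retention cut-offs are one day off the SAP's own day numbering, so a last dose on Day 90, 180 or 330 is classed differently in different sections

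*SAP*

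**What the plan says.** **Day numbering.** SAP 3.2.1 computes the relative day of an on-treatment date as the date minus the first BRV date plus 1: "Hence, the first day of BRV administration is Day 1".

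**Primary variable.** Under SAP 8.1.1 a patient is not retained at 12 months if either of two conditions is met: "Date of study termination < date of first BRV administration + 330 days" or "Date of last administration of BRV while in the study < date of first BRV administration + 330 days". The section ties the 330 days to the visit-window instruction given to sites and describes it as a 30-day tolerance around a 360-day target.

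**Secondary retention.** SAP 8.2.1 uses the same form: "Date of last administration of BRV while in the study < date of first BRV administration + 90 days" and "Date of last administration of BRV while in the study < date of first BRV administration + 180 days", each with a matching study-termination criterion. It explains the 3-month cut-off by saying that a patient who comes early and "terminates BRV prior to Day 90, would not be classed as having 3 months retention". The 6-month explanation is worded in parallel with Day 180.

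**Other places that use the same thresholds.**

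- Table 8-1, footnote [a], sets the seizure-freedom target days at Days 90 and 180, and "Visit 4 (Month 12) = Day 330".
- SAP 10.1 counts exposure as last dose minus first dose plus 1. It places 90 days in the 3-month category, 180 days in the 6-month category, and 330 days in "≥12 months BRV (≥330 days)".
- SAP 3.2.2 defines the Month 12 window as 330 or more days after the first BRV date.

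**The concern.** Two day counts are in use. The retention formulas count elapsed days from the first dose. The relative-day rule, the Table 8-1 targets and the exposure categories count the first dose as Day 1. The two differ by one day, and every threshold sits on the boundary.

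At 3 and 6 months this is a contradiction inside one section: the 8.2.1 formulas fail a patient whom the 8.2.1 explanation passes. At 12 months the primary rule matches one part of the SAP (3.2.2) and disagrees with two others (Table 8-1 and 10.1).

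What is at stake is the classification of any patient whose last dose falls exactly on the target day, and visibly discordant outputs. The by-patient retention listing in 8.1.1 prints time to discontinuation, which 8.1.2 computes with + 1, beside retention status. The same row could therefore show 330 days and not retained.

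**Working it through.** **Inputs.** Relative day = date − first + 1 (SAP 3.2.1). Retention fails if last dose or study termination < first + K, with K = 90, 180 (8.2.1) or 330 (8.1.1). Exposure = last − first + 1, with categories 1 to <90, 90 to <180, 180 to <330 and ≥330 days (10.1). Targets are Days 90, 180 and 330 (Table 8-1).

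**Step 1: put the cut-offs on the relative-day scale.** The date first + K is Day (first + K) − first + 1 = Day K + 1. The earliest last-dose days that pass are therefore Days 91, 181 and 331, against stated targets of Days 90, 180 and 330. The formulas do not reproduce the stated targets.

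**Step 2: classify a last dose one day before, on, and one day after each target.** A last dose on Day d is the date first + (d − 1).

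| Target | Last dose | Retained by formula | Exposure (days) and category | Stopped before Table 8-1 target? | Retained if cut-off is first + (K − 1) |
|---|---|---|---|---|---|
| 90 | Day 89 | No | 89, 1 to <90 | Yes | No |
| 90 | **Day 90** | **No** | **90, 90 to <180** | **No** | **Yes** |
| 90 | Day 91 | Yes | 91, 90 to <180 | No | Yes |
| 180 | Day 179 | No | 179, 90 to <180 | Yes | No |
| 180 | **Day 180** | **No** | **180, 180 to <330** | **No** | **Yes** |
| 180 | Day 181 | Yes | 181, 180 to <330 | No | Yes |
| 330 | Day 329 | No | 329, 180 to <330 | Yes | No |
| 330 | **Day 330** | **No** | **330, ≥330** | **No** | **Yes** |
| 330 | Day 331 | Yes | 331, ≥330 | No | Yes |

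All rules agree on the day before and the day after. They disagree only on the target day, so the conflict is exactly one day wide. The 12-month exposure label is involved only for Day 330; Days 90 and 180 conflict with the 3- and 6-month categories.

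**Step 3: check 8.1.1 against 3.2.2.** The Month 12 window opens at first + 330, which is Day 331. If last dose and study termination are both on that date, neither is earlier than first + 330, so the patient is retained. Rule and window agree.

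**Step 4: size per patient.** A patient is reclassified when the earlier of last dose and study termination falls on the target day. One such patient moves the retention percentage by:

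- 1/385 = 0.26 points at the planned FAS of 385;
- 1/477 = 0.21 points at an assumed FAS of 477 (530 × 0.90);
- 1/530 = 0.19 points if all 530 enter the FAS.

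As an illustration at n = 385, 192 retained is 49.9% (Clopper-Pearson 44.8 to 55.0). Moving 1 patient gives 50.1% (45.0 to 55.2); moving 5 gives 51.2% (46.1 to 56.3). The counts of 1 and 5 are not estimates.

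**Step 5: rough order of magnitude at 3 and 6 months.** Assume FAS 477, 50% retention at 330 days and a constant hazard. The daily hazard is ln 2/330 = 0.00210, and 477 × 0.00210 = 1.00. Expected stops are 1.00 × exp(−0.00210 × 90) = 0.83 on Day 90 and 1.00 × exp(−0.00210 × 180) = 0.69 on Day 180. Stops that cluster at visits would change these figures.

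**Step 6: planned precision.** 1.96² × 0.25/0.05² = 384.1, so 385, with half-width 0.0499. This reproduces and is unaffected.

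**The case against.** The strongest defence concerns the primary variable. The 8.1.1 formula is unambiguous, can be programmed as written, and matches both the 3.2.2 window and the instruction that 8.1.1 says sites received. All three are on an elapsed-day scale. This stands, and it rules out three stronger readings.

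- A reader might infer that a completer seen on the first permitted day is counted as a primary failure. The first permitted day is first + 330, and that patient passes. A visit on Day 330 is one day before the window opens.
- A reader might infer that a Visit 4 on Day 330 falls between the Day 136–329 mapping window and Month 12 in 3.2.2. That follows only if the mapping windows are relative days. Read as elapsed days, like the adjoining Month 12 limit, 136–329 and 330 onward are contiguous.
- A reader might infer that several patients, or more than a point of retention, are at stake. The documents give no distribution of visit dates and do not show how often a completer's last in-study dose is recorded for the day before Visit 4. The latter is a separate question of dose recording.

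Two further objections are fair. Measured against the 360-day target in 8.1.1, the 330-day rule is already lenient, so the one-day mismatch cannot be called a downward bias against a true 12 months. And exposure and retention tables need not agree in full: exposure is on the SS and the modified FAS, primary retention is on the FAS, and retention also depends on study termination. The discrepancy can still appear on the modified FAS, where both are tabulated, and in the listings.

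One could also argue that Day 90 in 8.2.1 is used loosely for 90 elapsed days. But the SAP defines Day 1 as the first dose in 3.2.1 and repeats it in 10.1, so the section should be read with that definition.

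**Conclusion.** The inconsistency is real and small. At 3 and 6 months the 8.2.1 formulas fail patients whose last dose is on Day 90 or Day 180, against that section's own explanation, Table 8-1 and 10.1. This needs no assumption beyond the SAP's definition of Day. At 12 months the primary rule is consistent with 3.2.2 but not with Table 8-1 or 10.1, so a last dose on Day 330 is 12-month exposure without 12-month retention.

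Each affected patient is worth about 0.2 to 0.3 percentage points, for a FAS between 385 and 530. The number affected is unknown. It is probably small because only a single day is involved. The planned sample size and confidence-interval width do not change.

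**What to change.** **3 and 6 months.** In SAP 8.2.1 replace + 90 by + 89 and + 180 by + 179 days in both criteria. Equivalently, require last − first + 1 to be at least 90 or 180, and the same for study termination. The explanatory text, Table 8-1 and 10.1 then need no change.

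**12 months.** Put 3.2.2, 8.1.1, Table 8-1 and 10.1 on one stated day count, by either route:

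1. Relative Day 330 throughout: + 329 days in both criteria of 8.1.1, the 3.2.2 Month 12 analysis window stated as relative Day 330 or later, and Table 8-1 and 10.1 left alone.
2. Keep 8.1.1 and 3.2.2 and say explicitly that they count elapsed days. Move the Table 8-1 target to Day 331 and the 10.1 boundary between the 6- and 12-month categories to 331 days.

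In either case state the scale of the 3.2.2 mapping windows.

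**Cost.** A few constants and some SAP wording. Route 1 has a small downside: it loosens the primary cut-off by one day after three snapshot analyses, and relative to the visit instruction already given to sites. If it is chosen, record the change and list the patients reclassified. The same record is sensible for the 8.2.1 change. Route 2 leaves the primary definition untouched.

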#### 8.1.2 Sensitivity analysis of the primary variable retention at 12 months

The 12 month retention analysis described in [Section 8.1.1](#) will be repeated on the modified FAS as a sensitivity analysis to represent the retention of patients who take BRV per the SmPC.

In addition, a Kaplan-Meier analysis of time to discontinuation of BRV or study termination will be provided on the FAS and the modified FAS. Time to discontinuation of BRV or study termination will be calculated as:

Minimum of (Date of last administration of BRV while in the study, Date of study termination) – date of first BRV administration + 1

A patient will be considered as having an event if the patient discontinues from the study (Study Termination [Dropout] CRF page completed) or if the patient is not prescribed Brivaracetam

after exiting the study (ie, answer to the CRF question “Will the subject be prescribed Brivaracetam after exiting the EP0077 study?” is “No”). All other patients will be considered as not having an event and will be censored at the date of study termination. For snapshot analyses, patients ongoing in the study will be censored at the date of data cut off.

The median time to event (days) will be presented along with the 25% and 75% quartiles and 95% CIs. In addition, the cumulative number of events, number at risk and survival estimate at monthly intervals will be provided. The Kaplan-Meier plot and raw statistical procedure output will be produced for the Kaplan-Meier analysis.

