## **6 EXPECTED STUDY DURATION, PLANNED NUMBER OF PATIENTS AND SITES**

It is planned to include 530 patients (see [Section 12.4](#)).

Approximately 100 sites are planned for participation. The overall expected enrollment period is approximately 3 years, but this may vary in the different countries depending on the respective start of commercial BRV availability.

The Observation Period per patient will be up to 12 months after initiation of BRV treatment.

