### 3.2.2 Visit 4, Month 12/Withdrawal Visit

Patients with early study termination (ie, those who complete the Study Termination [Dropout] CRF page), will have their Visit 4 (Month 12/Withdrawal) visits prior to the preferred visit window for Month 12 of greater than or equal to 330 days after date of first BRV administration. Patients completing the study (ie, those who complete the Study Termination NIS [Completed Subject] CRF form), will have their Visit 4 (Month 12/Withdrawal) visits within the preferred visit window for Month 12 of greater than or equal to 330 days after date of first BRV administration. Therefore, Visit 4 will be analyzed as follows depending on the objective and variable being analyzed:

- Visit 4 (Month 12): Including only patients who are study completers with a Visit 4 within the preferred visit window for Month 12 of greater than or equal to 330 days after the date of first BRV administration.
- Visit 4 (Month 12/Withdrawal): Including all data recorded at Visit 4 (ie, completers or patients who withdraw early)

In addition, Visit 4 (Month 12/Withdrawal) visits that correspond to scheduled visits will be included in the counts for the scheduled visits to which they correspond. To be classed as corresponding to the scheduled visit, the withdrawal visit must fall into the windows provided below and the patient have no scheduled visit already available. Only the variables below will have the mapping of withdrawal visits applied.

Variables	Visit 2, Month 3	Visit 3, Month 6
Disposition (Patients attending each visit)	30-135	136-329
Seizure Frequency	30-135	136-329
QOLIE	30-135	136-329
CGIC/PGIC	30-135	136-329
EpiTrack	No mapping as no scheduled visit	150-210

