## 5 STUDY POPULATION CHARACTERISTICS

### 5.1 Subject disposition

The following tables will be produced on the All Subjects Documented set:

- Disposition of All Subjects Documented. For all study sites and by study site, this table will show the date of the first patient in/last patient out and the number of patients in the All Subjects Documented set, FAS, SS and modified FAS.
- Disposition of Analysis sets to include the number and percentage of patients in the All Subjects Documented set, FAS, SS and modified FAS
- Disposition and Discontinuation Reasons including:
  - Number and percentage of patients completing or prematurely discontinuing the study with discontinuation reason (as recorded in the Study Termination NIS (Dropout) and Study Termination NIS (Completed Subject) CRF pages)
  - Number and percentage of patients continuing or discontinuing BRV after study participation in this NIS with discontinuation reason (as recorded in the Post-Study Treatment Continuation and Medication Discontinuation CRF pages)
- Number and percentage of patients attending each scheduled visit (including mapping of withdrawal visits as described in [Section 3.2.2](#))

In addition to a study eligibility criteria text listing, the following by-patient listings on the All Subjects Documented set will be produced:

- Patients who did not meet study eligibility criteria
- Patient disposition (including first and last BRV dose, completion and early discontinuation information, primary reason for discontinuation, whether the patient is prescribed BRV after exiting the study and the main reason for BRV discontinuation)
- Patient discontinuation (only including patients who discontinue)
- Patient analysis sets
- Patients excluded from analysis sets with reason for exclusion
- Visit dates

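### In the SAP 8.1.2 Kaplan-Meier analysis the exit answer on future BRV decides whether a completer is an event or is censored, so the curve after Day 330 can fall too low and give a spurious median

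*SAP*

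**What the plan says.** SAP 8.1.2 plans a Kaplan-Meier analysis of time to BRV discontinuation or study termination, on the FAS and the modified FAS, to support the 12-month retention proportion. Time runs from first BRV to the earlier of last BRV and study termination, plus 1. Dropouts are events. A completer is also an event "or if the patient is not prescribed Brivaracetam" after exit, according to a CRF question. For the rest: "All other patients will be considered as not having an event and will be censored at the date of study termination".

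No end day is set for the outputs: "The median time to event (days) will be presented along with the 25% and 75% quartiles and 95% CIs", and the "number at risk and survival estimate at monthly intervals will be provided".

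Three other places matter:

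- **Exit timing.** SAP 3.2.2 puts completers' last visit "within the preferred visit window for Month 12 of greater than or equal to 330 days after date of first BRV administration". No upper limit is given, and SAP 2.3 leaves visit timing to routine practice. Protocol 6 does say "The Observation Period per patient will be up to 12 months after initiation of BRV treatment", and SAP 8.1.1 mentions a 360-day target.
- **The 12-month mark.** SAP 8.1.1 says "330 days is used to represent 1 year of treatment" and classifies patients by dates only. The exit answer plays no part in the primary variable.
- **Post-study BRV.** SAP 5.1 already plans the "Number and percentage of patients continuing or discontinuing BRV after study participation in this NIS".

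**The concern.** Kaplan-Meier assumes that a censored patient has the same future risk as those still at risk. After Day 330 that fails. Protocol 8.2 withdraws a patient whose physician permanently stops BRV, so a completer's 'No' is essentially a decision made at exit. A 'Yes' completer is censored just after passing that decision. Those still at risk have not yet been asked. Each later 'No' is then divided by a risk set from which the 'Yes' answers have been removed.

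For example, with the curve at 0.60 and 10 patients left at risk, one 'No' lowers it by 0.60 × 1/10 = 6 points. That patient is 1/477 = 0.2 points of the FAS.

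At stake is a reported median (or quartile) somewhere after Day 330. It would read as half of patients having stopped BRV, next to a primary proportion that says otherwise.

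**Working it through.** **The plan's own figure.** SAP 2.4: 1.96² × 0.5 × 0.5 / 0.05² = 384.15, so 385, as stated. The documents give no figure for the Kaplan-Meier analysis.

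**Inputs.** From the documents: N = 530 less about 10% = 477; sizing proportion 0.50; completers exit from Day 330. Assumed, because the documents are silent: 'No' share of completers p = 2, 5 or 10%; retention at Day 330 of 60% or 70%, alongside the plan's 50%; exits uniform on Days 331–401 or 331–366, or bell-shaped (mean 365, SD 15); no dropout after Day 330. 'No' completers are counted as stopping at exit.

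**Bias at a given day.** Let S be the value at Day 330 and G the share of completers not yet exited. The share not yet having a 'No' is S × [1 − p(1 − G)]. With exits in continuous time the product-limit curve tends to S × G^p. The bias is the difference.

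For S = 0.60, p = 5%, exits to Day 401, at Day 360: G = 41/71 = 0.577. Then G^0.05 = 0.9729, 1 − 0.05 × 0.423 = 0.9789, and 0.60 × (0.9729 − 0.9789) ≈ −0.36 points. Counting exits in whole days gives −0.34.

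Downward bias in points at S = 0.60, whole days, for p = 2/5/10%:

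| Exits | Day | Bias |
|---|---|---|
| to Day 401 | 360 | 0.14 / 0.34 / 0.64 |
| bell-shaped | 360 | 0.11 / 0.27 / 0.52 |
| to Day 366 | 360 | 1.0 / 2.5 / 4.5 |
| to Day 401 | 390 | 1.1 / 2.7 / 5.0 |

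For scale, the binomial 95% half-width at 477 is 1.96 × √(0.6 × 0.4/477) = 4.4 points. At Day 390 about 0.6 × 477 × 12/71 = 48 patients remain at risk.

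**Chance that a median is reported.** Simulation at N = 477, p = 2/5/10%. The last column is how often the share leaving the study still due to be prescribed BRV really is 50% or less.

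| Retained, exits | Median reported | Truly 50% or less |
|---|---|---|
| 50%, to 401 | 88 / 99 / 100% | 67 / 86 / 99% |
| 60%, to 401 | 15 / 60 / 98% | 0 / 0.2 / 4% |
| 60%, to 366 | 11 / 55 / 98% | as above (does not depend on exit spread) |
| 70%, to 401 | 3 / 23 / 78% | 0% |

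At 60% retained and exits to 401, the typical number at risk when the median is reached is 7/15/48.

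**Checks.** With p = 0 there is no bias and no median at 60% retained. With all exits on one day (p = 5%) the bias is 0.00 and a median appears in 0.1% of runs, equal to the true rate. If 'No' records a real earlier stop dated at last dose, Day 360 bias is within 0.03 points. Ending the outputs at Day 330 gives a median in 0.0% of runs at 60% and 70% retained.

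**The case against.** **The drivers are assumed.** This stands. The only retention figure in the documents is 0.50. There most medians are genuine: the spurious excess is about 88 − 67 = 21, 99 − 86 = 13 and 100 − 99 = 1 points, with rounding and simulation error of about a point. The problem bites when retention is clearly above one half and several percent answer 'No'.

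**Exits to Day 401 go beyond the planned observation period.** Fair, given Protocol 6. But exits ending at Day 366 give almost the same chance of a spurious median, and a larger bias at Day 360.

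**The planned outputs warn the reader.** Partly true. With a log-log type interval (assumed, as the SAP names none), 60% retained and exits to 401, the upper limit of the median was not estimable in 99.5/96/51% of runs that reported one. The number at risk also shows a thin tail. Neither corrects the estimate, and the warning is weakest at 10% 'No'.

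**Nothing is observed after exit.** Correct. The benchmark is the share of patients still due to be prescribed BRV at exit, not the share known to have continued.

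**Stronger readings.** A reader might infer that the primary retention result is biased. It is not: 8.1.1 uses dates only. Nor is the whole curve unreliable: with completers exiting at Day 330 or later, nothing before that day changes.

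**Conclusion.** The concern holds for the late tail of a descriptive sensitivity analysis. Two conditions are needed together: some completers answer 'No' as an exit decision, and exits are staggered. Staggering follows from the visit rules. SAP 5.1 foresees post-study discontinuation, but its frequency is unknown. When both hold, the curve after Day 330 is biased downward.

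The bias is usually below 1 point at Day 360, reaching about 4.5 points if exits end by Day 366 and 10% answer 'No', and it grows later. The practical harm is a spurious median: likely at 60% retained with 5% or more 'No', or at 70% with about 10%, and small in excess at 50%. It would be wrong to say that any median after Day 330 is spurious, or that the size is known from the documents. The change is worth making because the rule as written produces the error and the remedy is simple.

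**What to change.** In SAP 8.1.2, state that Kaplan-Meier estimates, median, quartiles, confidence intervals and plot are reported only up to Day 330, the SAP's own 12-month mark, and that a quantile not reached by then is shown as not reached. In the disposition table of SAP 5.1, report 'No' completers as a proportion of all completers.

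The event and censoring rules need not change. It is tempting to re-censor everyone by the 8.1.1 date criteria instead. That would turn a completer who exits before Day 330 with 'Yes', who is now censored, into an event, so it is better avoided.

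Cost: two or three sentences and a re-run, with no new data. Discontinuations after Day 330 leave the curve. The Day 330 estimate then largely repeats the primary proportion, so what the curve adds is the timing of earlier discontinuation.
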